4. TIME-RELATED TERMS

4.1. Baseline and Screening Visit

The *Baseline/Screening Visit* for this study is the same as the Screening Visit of the INN-005 study. The terms screening and baseline are used interchangeably in this SAP.

4.2. Study Day

The *study day* describes the post-operative day or the relative day of an observation starting with the surgery date of the INN-005 study designated as Study Day 0. Thus, the study day in this study will be consistent with that of the INN-005 study.

4.3. Analysis Visit and Analysis Window

Analysis visit is a timing variable to be used for analyses involving visits. Typically, for each analysis visit, an analysis window is set up to determine the analysis visit to which a measurement should be mapped. However, no study assessments are required at unscheduled visits; hence, the analysis visit of measurements is the same as the study visit at which the measurements were collected. The analysis window, specified in Table 2, will be used to categorize the timing of adverse events, serious adverse events and post-operative interventions that did not necessarily fall into the listed protocol visit windows.

Table 2: Analysis Visit and Visit Window

Analysis Visit Name (Target Day)	Protocol Visit Window (for study measurements)	Analysis Window (for AEs, SAEs, interventions)
Baseline (Screening)	[,-1]	[,-1]
Month 36 (Day 1080)	[990, 1170]	[781, 1170]
Month 48 (Day 1440)	[1350, 1530]	[1171, 1530]
Month 60 (Day 1800)	[1710, 1890]	[1531,]

Confidential Page 14 of 32

5. GENERAL CONSIDERATIONS

There are two study groups in this study: treatment and control group. The treatment and the control group consist of all subjects who received PRESERFLO® MicroShunt device and trabeculectomy as part of the INN-005 study, respectively. All measures will be summarized by cohort and study group descriptively. Continuous variables will be summarized using descriptive statistics such as number of observations (n), mean, standard deviation, median, minimum, and maximum. Categorical variables will be tabulated using frequency (n) and percent (%).

Unless otherwise specified, the following conventions will be followed in reporting the decimal places.

Statistics	How to report statistics
Range (Low Value, High Value)	Recorded Decimal Places
Mean, Median	Recorded value + 1 Decimal Place
Confidence Interval, Standard Deviation, Standard Error	Recorded value + 1 Decimal Place
P-value	4 Decimal Places (ex. 0.0021)

Due to the nature of this study, there is no (confirmatory) label-claiming hypothesis testing foreseen in a strict statistical sense. Analyses are descriptive in nature and 95% (Wald) confidence intervals are used for exploratory purposes.

All data summary/analysis will be performed using SAS Version 9.4 or later. Individual data, including relevant derived variables, will be listed.

Additional analyses not specified in this SAP, including consistent cohort analysis, may be conducted if deemed necessary and will be documented in the CSR.

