5.1. Study Design Overview

The study is a prospective, concurrent controlled, open-label, multicenter study designed to collect safety data through 5 years of follow-up for subjects randomized to either the treatment arm (PRESERFLO® MicroShunt with MMC) or the control arm (Trabeculectomy with MMC) of the INN-005 clinical study. All subjects who have completed the Month 24 Follow-Up Visit for the INN-005 study, will be assessed for their eligibility to be enrolled in this long-term follow-up study, and will be required to return for up to three (3) follow-up visits through post-operative Month 60, i.e., at Month 36, Month 48, and Month 60 (follow-up visit timepoints to be calculated from subjects' Operative Visit in the INN-005 study). Subjects will still be eligible to enroll if they have already passed any of the earlier follow-up visit windows. At a minimum, subjects enrolled in the PRESERFLO® MicroShunt Extension Study should be able to complete the Month 60 Follow-Up Visit.

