7.2. Inclusion Criteria

To qualify for enrollment in this study, subjects must meet all of the following inclusion criteria:

- Subject has completed the Month 24 Follow-Up Visit in the INN-005 clinical study conducted under IDE G130028.
- Subject was randomized into the INN-005 study and received the PRESERFLO® MicroShunt device or trabeculectomy. (Subjects who have had the device explanted, or replaced with another device, may be included).
- Subject is willing and able to comply with all study requirements, including signing an informed consent form.

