9.3.2. Eligibility Assessment

After consent has been obtained, subjects will be screened for study eligibility according to the Inclusion and Exclusion criteria. Subjects deemed eligible for participation in the study, as well as screen failures, will be entered in the subject Screening and Enrollment Log. Subjects previously randomized to PRESERFLO® MicroShunt, and who had the device explanted or another device implanted, will be considered to be eligible for enrollment in this study and will not be a screen failure. For those subjects displaying mental confusion and/or signs of significant dementia, the Principal Investigator should make a determination as to whether or not the subject is able to comply with all study requirements per Inclusion criterion #3.

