6.1. Enrolled Population

The Enrolled population will include all subjects who were randomized in Phase II of the INN-005 study, completed the Month 24 Visit of the INN-005 study, signed the Informed Consent Form for the INN-005-EXT study, and enrolled in the study. This will be the primary analysis population; all effectiveness and safety outcome measure analyses will be based on the Enrolled population.

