8. EFFECTIVENESS ANALYSES

8.1. Effectiveness-Related Definitions

8.1.1. Study Eye and Fellow Eye

The study eye of a subject is the eye that received either the PRESERFLO® MicroShunt with MMC or underwent trabeculectomy with MMC in the INN-005 study. Hence, the study eye in this study is the same as the study eye in the INN-005 study. The other eye is the non-study eye, or the fellow eye.

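### SAP 5 forms the groups by procedure received, not by randomised arm, so an index-surgery crossover would enter the effectiveness comparisons as treated, with no as-randomised analysis and no listing of mismatches

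*SAP*

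**What the plan says.** The group-forming rule is one sentence in SAP 5: "The treatment and the control group consist of all subjects who received PRESERFLO® MicroShunt device and trabeculectomy as part of the INN-005 study, respectively". SAP 5 then has all measures summarised by study group, so the rule reaches every table.

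The protocol describes the same groups by assignment. Section 5.1 says that safety data are collected "for subjects randomized to either the treatment arm (PRESERFLO® MicroShunt with MMC) or the control arm (Trabeculectomy with MMC) of the INN-005 clinical study", and sections 3.2 and 7.1 describe them in the same way.

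Eligibility is set in Protocol 7.2: "Subject was randomized into the INN-005 study and received the PRESERFLO® MicroShunt device or trabeculectomy". The criterion adds in brackets: "Subjects who have had the device explanted, or replaced with another device, may be included". Protocol 9.3.2 identifies the explanted or replaced cases by their randomised arm: "Subjects previously randomized to PRESERFLO® MicroShunt, and who had the device explanted or another device implanted, will be considered to be eligible".

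SAP 6.1 defines the primary analysis population: "The Enrolled population will include all subjects who were randomized in Phase II of the INN-005 study, completed the Month 24 Visit", followed by consent and enrolment in the extension. SAP 6.2 removes subjects with deviations that affect effectiveness. Both sections settle who is analysed. Neither settles in which group.

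SAP 8.1.1 defines the study eye as "the eye that received either the PRESERFLO® MicroShunt with MMC or underwent trabeculectomy with MMC in the INN-005 study". It too speaks of the procedure received and does not name the index surgery.

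**The concern.** Assigned arm and procedure received agree for a subject who had the allocated operation. They part for a subject who was allocated one operation and given the other. The SAP sentence moves that subject to the other group in every table, effectiveness included, while the protocol's description keeps the subject in the arm that was drawn.

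What is at stake is the reading of the effectiveness differences. A change of procedure at surgery may be linked to the state of the eye, and hence to prognosis. Grouping by assignment prevents such a change from altering the composition of the groups; grouping by procedure received does not. Readers will tend to take a MicroShunt versus trabeculectomy difference from this extension as a comparison of the INN-005 randomised arms, and nothing in the planned output would tell them that some subjects had been re-sorted.

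For safety the issue is smaller. Attributing events to the operation actually performed is a common and defensible choice, but the SAP should say that it means the first operation.

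**Working it through.** The plan states no figure on this point, so there is nothing to reproduce. The check sets the texts side by side.

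**1. Is there another rule for group membership?** SAP 3.2 notes that subjects were previously randomised but does not use this to form groups. SAP 6.1 and 6.2 give no rule for a subject whose operation differed from assignment. SAP 5 is the only one.

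**2. When do the two definitions disagree?** (M = MicroShunt, T = trabeculectomy)

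| Randomised | Day 0 procedure | Later event in INN-005 | Group by randomisation | Group by SAP 5 |
|---|---|---|---|---|
| M | M | none | M | M |
| T | T | none | T | T |
| M | T | none | M | T |
| T | M | none | T | M |
| M | M | reoperation with T | M | M if the initial procedure is meant; the bare words also fit T |

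Rows 3 and 4 are admitted by Protocol 7.2, which asks for randomisation and for one of the two procedures without linking them.

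**3. Which effectiveness results depend on it?** Those with a between-group difference and 95% interval: total treatment success (SAP 8.3.1), mean percent change in IOP (8.3.2), qualifying interventions (8.3.3), medication responder rates (8.3.4), and total, complete and qualified success (8.3.5). None has an as-randomised counterpart.

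**4. Would a mismatch be visible?** SAP 7.4 lists major, minor and fellow-eye deviations and exclusions from the per-protocol set. None of these is a comparison of assigned arm with Day 0 procedure. SAP 5 promises listings of individual data in general but does not name this one.

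**5. What happens to row 5?** These rules bear on it:
- SAP 8.1.4.2.1 and 8.1.5: a later trabeculectomy is a failure of the original INN-005 procedure.
- SAP 8.3.1: such a subject is a non-responder.
- SAP 5.2.2 and 8.3.2: IOP after a glaucoma reoperation is censored.

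These rules make sense only if the eye keeps its first group. (SAP 8.3 and 8.3.1 cite 8.1.4.3 for the failure definition, which stands in 8.1.5; the slip does not change the inference.) They do not directly govern the adverse event summaries, where subjects continue to be followed after reoperation (Protocol 11.1 and 14.3), so an explicit statement is still useful there.

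**6. How large could the effect of rows 3 and 4 be?** Take *x* subjects who crossed from an arm of *N* with *S* successes to an arm of *M* with *T* successes, and let *s* of the *x* be successes. Then:
- Arm left: (S − s)/(N − x) − S/N = [x/(N − x)] × (S/N − s/x).
- Arm joined: (T + s)/(M + x) − T/M = [x/(M + x)] × (s/x − T/M).

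Both shifts are zero when x = 0. Otherwise they grow with the share that crossed and with the gap between the crossovers' success rate and that of each arm. If crossovers do worse than both arms, the arm they left looks better and the arm they joined looks worse. The documents give none of *x*, *s*, *N*, *M*, *S* or *T*, so no number can be put on it.

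**The case against.** **As-treated grouping suits the study.** Long-term safety is the objective and holds the primary outcome. This stands for the safety tables, and the fix keeps it there. It does not cover the effectiveness differences.

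**The study is descriptive.** No hypotheses are specified, intervals are exploratory, and no labelling claims are intended. The groups are already selected by Month 24 completion, new consent and the Phase II restriction (SAP 6 and 6.1), so no wording restores full randomised balance. All of this stands and keeps the point minor. It does not justify a further departure from assignment that costs nothing to avoid.

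**No crossover is reported.** True: the two definitions may coincide for every subject. The plan should still say what happens if they do not.

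**The sentence may only be loose.** SAP 3.2 and Protocol 8.3 use nearly the same phrase about INN-005 for the procedure to which subjects were randomised, so the authors may have meant the assigned operation. That is plausible, but SAP 5 says *received*, and a programmer would follow it.

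**A stronger reading is tempting.** Trabeculectomy heads the list of reoperations, and eyes with an explanted or replaced device are eligible. A reader might infer that a MicroShunt eye reoperated with trabeculectomy will be counted as control, or in both groups. The documents do not support this: the rules in step 5 keep the eye in its original group, and Protocol 9.3.2 identifies explanted or replaced cases by their randomised arm.

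**Conclusion.** The point holds for index-surgery crossovers. SAP 5 groups by procedure received, the protocol describes the arms by randomisation, and eligibility does not force the two to agree. Such a subject would be analysed as treated in all effectiveness differences, with no as-randomised result beside them and no listing to reveal the mismatch.

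For reoperated eyes the defect is only that SAP 5 does not say *initial procedure*: a wording gap, not a planned double count.

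A reader might also conclude that the randomised comparison is broken. That goes too far: no confirmatory comparison is planned, the comparison is already weakened by selection into the extension, and no crossover is documented. The size is unknown and may be zero. The conclusion rests on the wording alone and assumes no crossover count. Minor severity; a free improvement.

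**What to change.** Replace the group-forming sentence in SAP 5 with four statements:

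1. For all effectiveness comparisons, a subject's group is the arm assigned by randomisation in INN-005.
2. For safety summaries, a subject's group is the procedure completed at the INN-005 surgery on Study Day 0, as dated in SAP 4.2.
3. Reoperation, explantation or replacement of the device never changes the group.
4. Every subject whose randomised arm and Day 0 procedure differ is listed, with the number per arm; if there are none, the report says so.

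The cost is SAP wording and one short listing from data already held from INN-005. No visit, assessment or sample size changes. If crossovers exist, the effectiveness difference may become slightly less favourable; if none exist, no result changes.

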5.1. Adjustments for Covariates

The effectiveness and safety outcome measures will be summarized descriptively; hence no covariate adjustment will be necessary.

5.2. Handling of Missing Data

5.2.1. Safety Outcome Measures

For both descriptive summaries and exploratory analyses of ECD measures and ECD response status, subjects in whom the anterior chamber is entered for non-MicroShunt related indications (e.g., reoperation with trabeculectomy, implantation of other glaucoma drainage device, iridotomy/iridectomy, cataract extraction), and subjects who had the entire MicroShunt explanted, will be censored (i.e., treated as missing) from analysis after the qualifying event. No imputation will be performed on missing or censored ECD data.

Descriptive summaries of other safety measures will be based on observed data only. No imputation of missing scores will be implemented.

Confidential Page 15 of 32

5.2.2. Effectiveness Outcome Measures

For subjects who received any qualified glaucoma reoperations, unless otherwise specified, their IOP data collected after the events will be censored (treated as missing) in effectiveness outcome measure analyses. The missing IOP response statuses due to the IOP being censored will be imputed using the Baseline-Observation-Carried-Forward (BOCF) approach (i.e., a non-responder imputation). Missing IOP measure and IOP response statuses due to other reasons will not be imputed as analyses will be based on only observed cases.

5.3. Multi-Center Studies

This is a multicenter study with approximately 25 centers, among which a maximum of 5 centers are planned to be outside of the United States (EU sites). Descriptive summaries of the demographics and baseline as well as effectiveness results may be provided for the United States (US) population and the EU population, respectively.

5.4. Multiple Comparisons / Multiplicity

For this study, there is no (confirmatory) label-claiming hypothesis testing foreseen. Analyses are descriptive in nature and 95% confidence intervals from statistical models are used for exploratory purposes. Hence, no multiplicity adjustment is needed.

5.5. Interim Analysis and Data Safety Monitoring Board

An annual interim analysis will be performed after the last subject completes his/her Month 36 and Month 48 Visit using all available data from these subjects. Descriptive statistics (mean, median, standard deviation, minimum, and maximum for continuous variables; counts and percentages for categorical variables) will be used to summarize the demographic data, screening characteristics, observed IOP, observed IOP response status, use of glaucoma medications, slit lamp examination findings, fundus examination findings, specular microscopy, ocular AEs, and SAEs for each study group.

A Data Safety Monitoring Board (DSMB) will meet at regularly scheduled intervals i.e., at least annually, to review the accumulated safety data for this trial. This board will share their observations and recommendations regarding safety trends based on safety data analysis reports provided at each meeting (with as much up-to-date information as possible). The meeting format, membership, and activities will be similar to that for the INN-005 study.

Confidential Page 16 of 32

6. ANALYSIS POPULATION

Due to the timing gap between the INN-005 and the INN-005-EXT study, very few subjects who were randomized in Phase I of the INN-005 study are actually eligible for the INN-005-EXT study. Therefore, all analysis populations in the INN-005-EXT will be based on subjects who were randomized in Phase II of the INN-005 study.

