8.2. Enrollment

All subjects who sign the Informed Consent Form will be considered enrolled in the study, even if they subsequently fail to meet the study eligibility criteria. All enrolled subjects will be entered onto the Screening and Enrollment Log and will continue to use the same subject identification (ID) number as originally enrolled under in the INN-005 study. Subjects who do not meet the eligibility criteria will be considered a screen failure and will be exited from the study. The reason(s) for screen failure will be recorded on the Screening and Enrollment Log.

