An Unanticipated Adverse Device Effect (UADE) is defined as any serious adverse effect on the health or safety or any life-threatening problem or death caused by, or associated with, a device, if that effect, problem, or death was not previously identified in nature, severity, or degree of incidence in the investigational plan or application (including a supplementary plan or application), or any other unanticipated serious problem associated with a device that relates to the rights, safety, or welfare of subjects.

13. Assessment of Safety

Adverse Events will be collected for all enrolled subjects beginning at the Enrollment (Screening) Visit until the subject completes the study. The Principal Investigator is responsible for ensuring that all adverse events observed by the Investigator or site staff, or reported by subjects, are properly captured and recorded on the Adverse Event Form.

ENROLLMENT:

All SAEs that occurred between the Month 24 Visit of the INN-005 study and the time of consent for the INN-005-EXT study, are still *ongoing* at the time of consent, and for which surgery, physical intervention, or medication changes was required, whether they are considered to be device- or procedure-related or not, will be documented as AEs at the Enrollment Visit.

All ocular AEs, for both the study and fellow eye, that occurred between the Month 24 Visit and the time of consent, that are still *ongoing* at the time of consent, and for which surgery, physical intervention, or medication changes was required, will be documented as AEs at the Enrollment Visit.

All SAEs and ocular AEs that occurred between the Month 24 Visit and the time of consent, for which, surgery, physical intervention, or medication changes was required, and which are *resolved* at the time of consent, shall be captured in the subject's Medical/Surgical history at the Enrollment Visit.

If the action taken to address an ongoing AE at the time of consent was to administer medication more than 30 days prior to consent, the concomitant medication should be recorded on the CRF.

FOLLOW-UP:

All SAEs occurring during the study from the time of consent for the INN-005-EXT study will be assessed at each of the follow-up visits. SAEs, whether they are considered to be device- or procedure-related or not, must be documented.

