21.1. Sample Size Considerations

All 629 subjects who were randomized into both Phase I and II of the INN-005 study, and have completed their Month 24 Follow-Up Visit, will be assessed for eligibility to participate in this long-term follow-up study. The sample size will therefore be dependent upon the number of subjects who are willing to participate in, and who meet the eligibility criteria for, this study.

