9.2. Analysis of Safety Outcomes

All the safety-related outcome measures will be summarized descriptively for each cohort of the Enrolled population by study group.

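### The SAP limits every analysis population to Phase II, so any Phase I subject who enrols is left out of the primary sight-threatening AE incidence, the AE tables and disposition

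*SAP*

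**What the plan says.** **Protocol.** Section 21.1 describes the recruitment pool as "All 629 subjects who were randomized into both Phase I and II of the INN-005 study" who have completed Month 24. The treatment-related inclusion criterion in section 7.2 has no phase limit: "Subject was randomized into the INN-005 study and received the PRESERFLO® MicroShunt device or trabeculectomy". Section 8.2 says "All subjects who sign the Informed Consent Form will be considered enrolled in the study", with those who fail eligibility then exited as screen failures. Section 13 says "Adverse Events will be collected for all enrolled subjects beginning at the Enrollment (Screening) Visit until the subject completes the study". The primary outcome in sections 4.2 and 21.2, the incidence of sight-threatening adverse events, carries no phase limit either. Section 21 leaves detailed analyses to the SAP.

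**SAP.** Section 3.3 repeats the two-phase pool of 629. Section 5 defines the two study groups as everyone who received the MicroShunt or trabeculectomy in INN-005. Section 6 then says that "all analysis populations in the INN-005-EXT will be based on subjects who were randomized in Phase II of the INN-005 study". The reason given is that the time gap between the two studies leaves very few Phase I subjects eligible. The definitions in 6.1 (Enrolled) and 6.2 (Per-Protocol) both carry the limit. Of the Enrolled population, 6.1 says: "This will be the primary analysis population; all effectiveness and safety outcome measure analyses will be based on the Enrolled population". Section 9.2.1 ties the primary incidence to that population by name. Section 9.2 asks for safety outcomes to be "summarized descriptively for each cohort of the Enrolled population by study group"; the SAP does not define 'cohort'.

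**The concern.** This is a descriptive long-term safety study with no hypothesis test to protect. A small Phase I group might be a reason not to analyse it on its own. It is not a reason to remove treated, consented subjects from a safety count, and the exact intervals in SAP 9.2.1 cope with small numbers. The primary outcome may be rare, so a single event left outside the population could change the reported rate visibly.

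There is also a labelling problem. In the protocol, enrolled means everyone who signed consent; in the SAP, the Enrolled population means Phase II only. Someone reading the study report could take a table headed Enrolled to cover everyone who joined.

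**Working it through.** The plan states no figure to reproduce: 629 is a headcount, and neither document splits it by phase or by arm. The check is a trace through the definitions, followed by an illustration.

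**Step 1. Follow one Phase I subject who completed Month 24, is still inside the Month 60 window, and consents.**

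| Question | Source | Answer |
|---|---|---|
| Eligible? | Protocol 7.2, 7.3 | Yes; no phase criterion |
| Enrolled under the protocol? | Protocol 8.2 | Yes |
| Adverse events collected? | Protocol 13 | Yes |
| In a study group? | SAP 5 | Yes |
| In the Enrolled or Per-Protocol population? | SAP 6, 6.1, 6.2 | No |
| In the primary incidence? | SAP 9.2.1 | No |
| In the AE tables? | SAP 6.1, 9.2 | No |
| In disposition? | SAP 7.1 read with 6.1 | No |

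No other safety set is defined, so the subject contributes 0 to the numerator and 0 to the denominator. The answers from SAP 5 and SAP 6 cannot both describe the analysed groups.

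**Step 2. Size, on assumed counts.** The method is the SAP's own Clopper-Pearson 95% interval for x events in n subjects:

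- lower limit = Beta quantile at 0.025 with parameters (x, n − x + 1), or 0 if x = 0;
- upper limit = Beta quantile at 0.975 with parameters (x + 1, n − x). For x = 0 this is 1 − 0.025^(1/n).

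For example, 1 − 0.025^(1/150) = 2.43% and 1 − 0.025^(1/155) = 2.35%.

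The assumptions, none of them document figures, are 75, 150 or 300 Phase II subjects in an arm and 5 Phase I subjects added.

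| Phase II, no events | Upper limit | Add 5, no event: upper limit | Add 5, one event: rate (95% CI) |
|---|---|---|---|
| 0/75 | 4.80% | 4.51% | 1/80 = 1.25% (0.03–6.77) |
| 0/150 | 2.43% | 2.35% | 1/155 = 0.65% (0.02–3.54) |
| 0/300 | 1.22% | 1.20% | 1/305 = 0.33% (0.01–1.81) |

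If Phase II already has one event, 1/150 = 0.67% (0.02–3.66) becomes 1/155 = 0.65% (0.02–3.54) when the added subjects have none, and 2/155 = 1.29% (0.16–4.58) when one of them has an event.

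Adding 2 or 10 subjects to 0/150 instead of 5 gives the same pattern. The upper limit is 2.40% or 2.28% with no event. With one event the rate is 0.66% (upper limit 3.61%) or 0.62% (upper limit 3.43%).

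**Reading.** Without an event among the Phase I subjects the restriction has almost no effect. With one, a zero rate becomes non-zero, or a single-event rate roughly doubles. The intervals overlap heavily throughout: what changes is whether an event is counted, more than the precision.

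**The case against.** The sponsor has several fair answers.

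- **The protocol defines no analysis set.** A reader might infer that it promises the primary incidence for both phases. It does not: it names a recruitment pool, sets the scope of AE collection and defers detail to the SAP, which discloses the restriction and gives a reason. This stands. The issue is a mismatch between who is followed and who is counted, not a broken commitment.
- **Nobody may be affected.** A reader might infer that followed Phase I subjects are in fact being dropped. The SAP says only that very few are eligible; no section shows that any consented. This stands, and it limits the size of the point.
- **Pooling has a cost.** It is tempting to say that the exclusion can only lose information. But the timing gap means Phase I subjects would tend to enter late, possibly after the Month 36 and 48 windows (Protocol 5.1). Events that arose after Month 24 and resolved before consent go to medical history, not to the AE record (Protocol 9.3.3 and 13). Such subjects fill the denominator with a shortened capture period and can dilute the rate. Late Phase II entrants share this, so it argues for separate columns rather than for exclusion.
- **Events would not be invisible.** Sight-threatening events reach the sponsor within 24 hours (Protocol 14.2.3). The DSMB reviews accumulated safety data with no stated phase limit (SAP 5.5). The listings in SAP 5, 9.2.1 and 9.2.2.1 are not expressly confined to Phase II, though none is expressly extended to Phase I. This softens the consequence, but none of these routes puts an event into the incidence.
- **'Cohort' is undefined.** One might read it as phase and conclude that the restriction makes the by-cohort summaries impossible. The SAP does not say that cohort means phase, so the text supports only a request to define the term.

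**Conclusion.** The point holds in a limited form. By the SAP's own definitions, any Phase I subject who enrols is absent from the primary sight-threatening AE incidence, the AE tables and disposition, although the protocol admits that subject and collects the data. SAP 3.3 and 5 conflict with SAP 6 to 6.2, and a small expected number does not justify the omission in a descriptive safety study.

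The size cannot be fixed from the documents. It is nil if no Phase I subject enrols, negligible if those who do have no event, and visible in a rare-event rate if one does. The figures shown rest on assumed arm sizes, Phase I counts and events. The change is worth making because it touches the primary outcome and costs little, not because a material distortion has been shown.

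**What to change.** In SAP 6, add a safety set: all eligible enrolled subjects from either phase (screen failures excluded) who received the MicroShunt or trabeculectomy in INN-005. For the primary incidence, the AE and SAE tables and listings, and disposition, show Phase II, Phase I and all enrolled subjects side by side. Keep the Phase II population for effectiveness.

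Also:

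- state the number of Phase I subjects enrolled in each arm, even if it is zero;
- define 'cohort' where SAP 5, 7.2 and 9.2 use it;
- reconcile SAP 3.3 and 5 with SAP 6 to 6.2, and make clear that the Enrolled population is narrower than enrolment under Protocol 8.2.

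If the sponsor prefers to leave the primary rate as Phase II only, the minimum is a separate Phase I AE table and listing with its denominator.

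The cost is SAP wording and extra table columns; no new data are needed. The downside is that late-entering Phase I subjects may slightly dilute the pooled rate. The separate columns let the reader see this.
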